9.2 Adverse Events

The definitions of an AE or SAE can be found in Appendix 3.

Immune-mediated adverse events (IMAEs) are AEs consistent with an immune-mediated mechanism or immune-mediated component for which non-inflammatory etiologies (eg, infection or tumor progression) have been ruled out. IMAEs can include events with an alternate etiology, which were exacerbated by the induction of autoimmunity. Information supporting the assessment will be collected on the participant's CRF.

AEs will be reported by the participant (or, when appropriate, by a caregiver, surrogate, or the participant's legally authorized representative).

The investigator and any designees are responsible for detecting, documenting, and reporting events that meet the definition of an AE or SAE and remain responsible for following up AEs that are serious, are considered related to the study treatment or the study, or caused the participant to discontinue before completing the study.

Contacts for SAE reporting are specified in Appendix 3.

9.2.1 Time Period and Frequency for Collecting AE and SAE Information

The collection of non-serious AE information should begin at the initiation of study treatment until 100 days of the last dose of study treatment, at the time points specified in the Schedule of Activities (Section 2).

Following the participant's written consent to participate in the study, all SAEs, whether related or not related to study treatment, must be collected, including those thought to be associated with protocol-specified procedures.

All SAEs that occur during the screening period and within 100 days of the last dose of study treatment must be collected. If applicable, SAEs that relate to any later protocol-specified procedure (eg, a follow-up skin biopsy) must be collected. For participants assigned to treatment and never treated with study treatment, SAEs should be collected for 30 days from the date of treatment assignment.

The investigator must report any SAE that occurs after these time periods and that is believed to be related to study treatment or protocol-specified procedure.

- Medical occurrences that begin before the start of study treatment but after obtaining informed consent will be recorded on the appropriate section of the CRF section.
- All SAEs will be recorded and reported to the Sponsor or designee within 24 hours, as indicated in Appendix 3.
- The investigator will submit any updated SAE data to the Sponsor within 24 hours of this being available.

An SAE report should be completed for any event where doubt exists regarding its seriousness.

If the investigator believes that an SAE is not related to study treatment, but is potentially related to the conditions of the study (such as withdrawal of previous therapy or a complication of a study procedure), the relationship should be specified in the narrative section of the SAE Report Form.

Investigators are not obligated to actively seek AEs or SAEs in former study participants. However, if the investigator learns of any SAE, including a death, at any time after a participant has been discharged from the study, and he/she considers the event reasonably related to the study treatment or study participation, the investigator must promptly notify the Sponsor.

The method of evaluating and assessing causality of AEs and SAEs and the procedures for completing and reporting/transmitting SAE reports are provided in Appendix 3.

9.2.2 Method of Detecting AEs and SAEs

Adverse events can be spontaneously reported or elicited during open-ended questioning, examination, or evaluation of a participant. Care should be taken not to introduce bias when collecting AE and/or SAEs. Inquiry about specific AEs should be guided by clinical judgement in the context of known adverse events, when appropriate for the program or protocol.

9.2.3 Follow-up of AEs and SAEs

- Non-serious AEs should be followed to resolution or stabilization, or reported as SAEs if they become serious (see Appendix 3).
- Follow-up is also required for non-serious AEs that cause interruption or discontinuation of study treatment and for those present at the end of study treatment as appropriate.
- All identified non-serious AEs must be recorded and described on the non-serious AE page of the CRF (paper or electronic). Completion of supplemental CRFs may be requested for AEs and/or laboratory abnormalities that are reported/identified during the course of the study.

After the initial AE/SAE report, the investigator is required to proactively follow each participant at subsequent visits/contacts. All SAEs will be followed until resolution, until the condition stabilizes, until the event is otherwise explained, or until the participant is lost to follow-up (as defined in Section 8.3).

Further information on follow-up procedures is given in Appendix 3.

9.2.4 Regulatory Reporting Requirements for SAEs

All SAEs that occur during the screening period and within 100 days of the last dose of study treatment must be collected. For participants randomized/assigned to treatment and never treated with study treatment, SAEs should be collected for 30 days from the date of randomization/treatment assignment.

- Prompt notification by the investigator to the Sponsor of SAEs is essential so that legal obligations and ethical responsibilities toward the safety of participants and the safety of a product under clinical investigation are met.
- An investigator who receives an investigator safety report describing SAEs or other specific safety information (eg, summary or listing of SAEs) from the Sponsor will file it along with the IB and will notify the Institutional Review Board/EC, if appropriate according to local requirements.

Sponsor or designee will be reporting AEs to regulatory authorities and EC according to local applicable laws including European Directive 2001/20/EC and FDA Code of Federal Regulations 21 CFR Parts 312 and 320. A suspected unexpected serious adverse reaction is a subset of SAEs and will be reported to the appropriate regulatory authorities and investigators following local and global guidelines and requirements.

9.2.5 Pregnancy

If, following initiation of the study treatment, it is subsequently discovered that a participant is pregnant or may have been pregnant at the time of study exposure, including during at least 5 half-lives after product administration, the investigator must immediately notify the BMS Medical Monitor/Study Director (or designee) of this event and complete and forward a Pregnancy Surveillance Form to BMS Designee within 24 hours of awareness of the event and in accordance with SAE reporting procedures described in Appendix 3.

In most cases, the study treatment will be permanently discontinued in an appropriate manner (eg, dose tapering if necessary for participant safety). Please call the BMS Medical Monitor/Study Director (or designee) within 24 hours of awareness of the pregnancy.

Protocol-required procedures for study discontinuation and follow-up must be performed on the participant.

Follow-up information regarding the course of the pregnancy, including perinatal and neonatal outcome and, where applicable, offspring information, must be reported on the Pregnancy Surveillance Form.

Any pregnancy that occurs in a female partner of a male study participant should be reported to the Sponsor or designee. For the Sponsor or designee to collect any pregnancy surveillance information from the female partner, the female partner must sign an ICF for disclosure of this information. Information on this pregnancy will be collected on the Pregnancy Surveillance Form.

9.2.6 Laboratory Test Result Abnormalities

The following laboratory test result abnormalities should be captured on the non-serious AE CRF page or electronic SAE Report Form, as appropriate. Paper forms are only intended as a back-up option when the electronic system is not functioning.

- Any laboratory test result that is clinically significant or meets the definition of an SAE
- Any laboratory test result abnormality that required the participant to have study treatment discontinued or interrupted
- Any laboratory test result abnormality that required the participant to receive specific corrective therapy

It is expected that, wherever possible, the clinical rather than laboratory term would be used by the reporting investigator (eg, anemia versus low hemoglobin value).

9.2.7 Potential Drug-induced Liver Injury

Wherever possible, timely confirmation of initial liver-related laboratory abnormalities should occur prior to the reporting of a p-DILI event. All occurrences of p-DILIs, meeting the defined criteria, must be reported as SAEs (see Section 9.2.4 and Appendix 3 for reporting details).

p-DILI is defined as:

- 1) Aminotransaminases (AT) (ALT or AST) elevation > 3× ULN AND
- Total bilirubin > 2× ULN, without initial findings of cholestasis (elevated serum ALP), AND
- 3) No other immediately apparent possible causes of AT elevation and hyperbilirubinemia, including, but not limited to, viral hepatitis, preexisting chronic or acute liver disease, or the administration of other drug(s) known to be hepatotoxic.

The key responsibilities for investigators during p-DILI assessment include the following:

- Early detection, medical evaluation (including the exclusion of other potential causes), and rapid laboratory confirmation of liver-related abnormalities
- BMS notification of p-DILI cases via SAE forms

Following the gathering and assessment of relevant clinical information, BMS is responsible for:

- Timely evaluation and triaging of p-DILI cases
- Expedited reporting of p-DILI cases
- Expanded review of p-DILI cases, including a detailed assessment of all available clinical information, investigations, and biochemical data

Investigators are expected to monitor ongoing routine and ad hoc hepatic laboratory test results to rapidly determine whether a participant meets p-DILI criteria. They are expected to promptly notify BMS of all p-DILI cases. p-DILI cases may be identified by abnormal liver biochemistry values, whether or not they are accompanied by liver-related signs and/or symptoms. In both cases, expedited confirmation with repeat laboratory testing should occur within 3 business days using a hepatic laboratory panel (ALT, AST, total bilirubin, and ALP). Any participant with an abnormal hepatic laboratory panel that meets p-DILI criteria is a candidate for study treatment discontinuation. Any confirmed p-DILI event must be reported (along with a description of the clinical findings) to BMS as an SAE within 24 hours of confirmation.

An extensive clinical history examination and appropriate investigations should be obtained to exclude cholestatic and other apparent causes that may explain the observed abnormalities in liver function and/or hepatic signs and symptoms. Other apparent causes include, nonexhaustively and by way of example only, infectious diseases (such as active hepatitis A, B, and C), congenital diseases (such as Gilbert's syndrome), neoplastic diseases (such as hepatocellular carcinoma), autoimmune diseases (such as primary biliary cirrhosis), and the use of concomitant hepatotoxic medications (such as antibiotics, the oral contraceptive pill, and herbal medicines). All investigations to exclude potential causes of liver function abnormalities or hepatic signs and/or symptoms should be guided by relevant factors such as the participant's age, gender, clinical history, and signs and symptoms.

9.2.8 Other Safety Considerations

Any significant worsening noted during interim or final physical examinations, ECG, x-ray filming, and any other potential safety assessment required or not required by protocol should also be recorded as a non-serious AE or SAE, as appropriate, and reported accordingly.

9.3 Overdose

An overdose is defined as the accidental or intentional administration of any dose of a product that is considered both excessive and medically important. For this study, any dose of BMS-986226, nivolumab and/or ipilimumab, that is greater than the assigned dose, and considered excessive and medically important by the investigator, will be considered an overdose.

In the event of an overdose, the investigator/treating physician should:

- 1) Contact the Medical Monitor/Study Director (or designee) immediately
- 2) Closely monitor the participant for AEs/SAEs and laboratory abnormalities until study treatment can no longer be detected systemically (at least 125 days)
- 3) Obtain a plasma sample for PK analysis within 125 days from the date of the last dose of study treatment if requested by the Medical Monitor/Study Director (or designee) (determined on a case-by-case basis)
- 4) Document the quantity of the excess dose as well as the duration of the overdosing in the CRF.

Decisions regarding dose interruptions or modifications will be made by the investigator in consultation with the Medical Monitor/Study Director (or designee) based on the clinical evaluation of the participant.

9.4 Safety

Planned time points for all safety assessments are listed in the Schedule of Activities (Section 2).

9.4.1 Physical Examinations

Refer to the Schedule of Activities for the timing of assessments (Section 2).

9.4.2 Vital Signs

Refer to the Schedule of Activities for the timing of assessments (Section 2).

9.4.3 Electrocardiograms

Refer to the Schedule of Activities for the timing of assessments (Section 2).

For the purposes of monitoring participant safety, the investigators will review the 12lead ECGs using their site's standard ECG machines throughout the study.

9.4.4 Clinical Safety Laboratory Assessments

- Investigators must document their review of each laboratory safety report.
- A central/local laboratory will perform the analyses and will provide reference ranges for these tests.
- Results of clinical laboratory tests performed on Day -1 must be available prior to dosing.
- The clinical tests that will be performed are shown in Table 9.4.4-1.
- Results of all laboratory tests required by this protocol must be provided to the Sponsor, recorded either on the laboratory pages of the CRF or by another mechanism as agreed upon between the investigator and BMS (eg, provided electronically). If the units of a test result differ from those printed on the CRF, the recorded laboratory values must specify the correct
units. Any abnormal laboratory test result considered clinically significant by the investigator must be recorded on the appropriate AE page of the CRF (see Section 9.2.6).

Hematology	
Prothrombin time, activated partial thromboplastin time	e, and international normalized ratio (at screening only)
Platelet count	Hemoglobin
Hematocrit	Total leukocyte count, including differential
Serum Chemistry	
Aspartate aminotransferase Alanine aminotransferase Total bilirubin Direct bilirubin (reflex only) Alkaline phosphatase Lactate dehydrogenase Creatinine Blood urea nitrogen Glucose (Fasting required at screening only) Gamma glutamyl transferase (reflex only) Lipase Testosterone (PRC only) C-reactive protein	Total protein Albumin Sodium Potassium Chloride Carbon Dioxide Calcium Phosphorus Magnesium Creatine kinase Creatinine clearance- screening only Thyroid stimulating hormone Free T3 and T4 (screening and reflex only) Amylase
Urinalysis	Dised
Protein	Blood
Glucose	Leukocyte esterase
Specific gravity	pH
Microscopic examination of the sediment if positive for blood, protein, or leukocytes esterase on dipstick	
Serology	

Serum for hepatitis C antibody (If hepatitis C antibody is positive reflex to hepatitis C RNA) or hepatitis C RNA, hepatitis B surface antigen.

Testing for HIV-1 and HIV-2 must be performed at sites only where mandated by local requirements. (Screening Only)

Viral Status HNSCC and CC only: Sites should submit and document prior HPV status and subtype, particularly HPV16 and HPV18, within 28 days of dosing.

Tetanus booster (administered 3-7 days prior to Cycle 1 Day 1 at screening; a tetanus booster does not have to be administered if the participant received a tetanus booster within 6 weeks of starting study drug)

Table 9.4.4-1:Clinical Laboratory Tests

Other Analyses	
Pregnancy test (women of childbearing potential only: screening, pre-dose, discharge).	

```
Follicle-stimulating hormone (screening only for women only)
```

9.4.5 Imaging Safety Assessment

Any incidental findings of potential clinical relevance that are not directly associated with the objectives of the protocol should be evaluated and handled by the study investigator as per standard medical/clinical judgment.

9.5 Pharmacokinetic and Immunogenicity Assessments

Samples for PK and immunogenicity assessments will be collected for all participants receiving BMS-986226, as described in Table 9.5-1 through Table 9.5-4. Immunogenicity samples will be analyzed for anti-BMS-986226 antibodies, by validated immunoassays.

All pre-dose samples should be taken within 30 minutes prior to the start of the infusion of first drug. End-of infusion (EOI) samples should be taken immediately prior to the stopping of the drug infusion (in monotherapy) or to the stopping of the second drug infusion (in combination therapy), preferably within 2 minutes prior to the end of infusion. On-treatment PK samples are intended to be drawn relative to actual dosing days. If a dose occurs on a different day within the cycle due to delays or minor schedule adjustments, PK samples should be adjusted accordingly. If it is known that a dose is going to be delayed, then the pre-dose sample should be collected just prior to the delayed dose. However, if a pre-dose sample is collected but the dose is subsequently delayed, an additional pre-dose sample should not be collected. Further details of sample collection, processing, and shipment will be provided in the Laboratory Manual.

Table 9.5-1:Pharmacokinetic and Immunogenicity Sampling Schedule for BMS-986226 (Preliminary Safety
Cohorts and Part A)

Study Day of Sample Collection (1 Cycle = 4 Weeks)	Event	Time (Relative to Start of BMS-986226 Infusion) Hour:Min	BMS-986226 Blood Sample	BMS-986226 Immunogenicity Sample
Treatment Cycles	· · ·	·		·
	Pre-dose	0:00	Х	Х
Cycle 1 Day 1 (C1D1) ^a	EOI ^b	0:30	Х	
		4:00	Х	
C1D2		24:00	Х	
C1D4		72:00	Х	
C1D8 (+/- 1 day)		168:00	Х	
C1D15 (+/- 1 day)		336:00	Х	Х
C1D22 (+/- 1 day)		504:00	Х	
	Pre-dose	0:00	Х	Х
C2D1	EOI ^b	0:30	Х	
		4:00	Х	
C2D2		24:00	Х	
C2D8 (+/- 1 day)		168:00	Х	
C2D15 (+/- 1 day)		336:00	Х	
C2D22 (+/- 1 day)		504:00	Х	
	Pre-dose	0:00	Х	X
C3D1	EOI ^b	0:30	Х	
C3D2		24:00	Х	

Table 9.5-1:Pharmacokinetic and Immunogenicity Sampling Schedule for BMS-986226 (Preliminary Safety
Cohorts and Part A)

Study Day of Sample Collection (1 Cycle = 4 Weeks)	Event	Time (Relative to Start of BMS-986226 Infusion) Hour:Min	BMS-986226 Blood Sample	BMS-986226 Immunogenicity Sample
C3D8 (+/- 1 day)		168:00	Х	
C3D15 (+/- 1 day)		336:00	Х	
C3D22 (+/- 1 day)		504:00	Х	
	Pre-dose	0:00	Х	Х
C4D1	EOI ^b	0:30	Х	
C5D1	Pre-dose	0:00	Х	Х
C6D1	Pre-dose	0:00	Х	Х
Adverse Event				
Grade 3/4 Hypersensitivity Reaction ^c			Х	Х
End of Treatment and Follow	v-up Period			
ЕОТ			Х	Х
30-Day FU			Х	Х
60-Day FU			Х	Х
100-Day FU			Х	Х

^a Participants taking 2 or 8 mg of BMS-986226 in the Preliminary Safety Cohorts will follow the same sampling schedule as in Part A. In the event that participants taking 2 or 8 mg of BMS-986226 should be permitted to intra-dose escalate up to 8 and/or 25 mg, the sampling schedule should be restarted at Cycle 1 Day 1 at each dose escalation.

^b This sample should be taken immediately prior to the stopping of the BMS-986226 drug infusion (in monotherapy), preferably within 2 minutes prior to the end of infusion. If the end of infusion is delayed beyond the nominal infusion duration, the collection of this sample should also be delayed accordingly. EOI samples may not be collected from the same IV access as the drug was administered.

^c Samples will be taken as directed when drug-related adverse event, Grade 3/4 infusion reaction, or hypersensitivity reaction is confirmed. Abbreviations: C = Cycle; D = Day; EOI = end of infusion; EOT = end of treatment; FU = follow-up.

Table 9.5-2:Pharmacokinetic and Immunogenicity Sampling Schedule for BMS-986226
(Parts B1 and C1)

Study Day of Sample Collection (Cycle = 4 weeks)	Event	Time (Relative to Start of Nivolumab or Ipilimumab Infusion) Hour:Min	BMS-986226 Blood Sample	BMS-986226 Immunogenicity Sample
Treatment Cycles				
Cycle 1 Day 1 (C1D1)	Pre-dose ^a	00:00	Х	X
(CIDI)	EOI ^b	00:30	Х	
		04:00	Х	
C1D2		24:00	Х	
C1D4		72:00	Х	
C1D8 (+/- 1 day)		168:00	Х	
C1D15 (+/- 1 day)		336:00	Х	
C1D22 (+/- 1 day)		504:00	Х	
C2D1	Pre-dose	0:00:00	Х	X
C2D8 (+/- 1 day)		168:00	Х	
C2D15 (+/- 1 day)		336:00	Х	
C3D1	Pre-dose	0:00	Х	X
	Pre-dose	0:00	Х	X
C4D1	EOI ^b	0:30	Х	
		4:00	Х	
C4D2		24:00	Х	
C4D8 (+/- 1 day)		168:00:00	Х	
C4D15 (+/- 1 day)		336:00:00	Х	

Table 9.5-2:Pharmacokinetic and Immunogenicity Sampling Schedule for BMS-986226
(Parts B1 and C1)

Study Day of Sample Collection (Cycle = 4 weeks)	Event	Time (Relative to Start of Nivolumab or Ipilimumab Infusion) Hour:Min	BMS-986226 Blood Sample	BMS-986226 Immunogenicity Sample
C4D22 (+/- 1 day)		504:00:00	Х	
C5D1	Pre-dose	0:00	Х	
C5D8 (+/- 1 day)		168:00	Х	
C5D15 (+/- 1 day)		336:00	Х	
C6D1	Pre-dose	0:00	Х	X
C7D1	Pre-dose	0:00	Х	X
C7D1	EOI ^b	0:30	Х	
C8D1	Pre-dose	0:00	Х	
	Pre-dose	0:00	Х	X
C10D1	EOI ^b	0:30	Х	
Every 3 Cycles starting with C13D1 (example: C16D1, C19D1, etc)	Pre-dose	0:00	Х	X
Adverse Event				
Grade 3/4 Hypersensitivity Reaction ^c			Х	
End of Treatment a	nd Follow-uj	p Period		-
EOT			Х	X
30-Day FU			Х	X

Table 9.5-2:Pharmacokinetic and Immunogenicity Sampling Schedule for BMS-986226
(Parts B1 and C1)

Study Day of Sample Collection (Cycle = 4 weeks)	Event	Time (Relative to Start of Nivolumab or Ipilimumab Infusion) Hour:Min	BMS-986226 Blood Sample	BMS-986226 Immunogenicity Sample
60-Day FU			Х	Х
100-Day FU			Х	Х

^a All pre-dose samples for BMS-986226 should be taken prior to the start of nivolumab/ipilimumab infusion (preferably within 30 minutes).

^b This sample should be taken immediately prior to the stopping of the second drug infusion (in combination therapy), preferably within 2 minutes prior to the end of infusion. If the end of infusion is delayed beyond the nominal infusion duration, the collection of this sample should also be delayed accordingly. EOI samples may not be collected from the same IV access as the drug was administered.

^c Samples will be taken as directed when drug-related adverse event, Grade 3/4 infusion reaction, or hypersensitivity reaction is confirmed.

Abbreviations: C = Cycle; D = Day; EOI = end of infusion; EOT = end of treatment; FU = follow-up.

Table 9.5-3:Pharmacokinetic and Immunogenicity Sampling Schedule for BMS-986226
(Parts B2 and C2)

Study Day of Sample Collection (1 Cycle = 4 Weeks)	Event	Time (Relative to Start of BMS-986226 Infusion) Hour:Min	BMS-986226 Blood Sample	BMS-986226 Immunogenicity Sample
Treatment Cycles				
Cycle 1 Day 1 (C1D1)	Pre-dose ^a	00:00	Х	Х
(0121)	EOI ^b	00:30	Х	
		04:00	Х	
C1D2		24:00	Х	
C1D4		72:00	Х	
C1D8 (+/- 1 day)		168:00	Х	
C1D15 (+/- 1 day)		336:00	Х	
C1D22 (+/- 1 day)		504:00	Х	
C2D1	Pre-dose	00:00	Х	Х
	EOI ^b ,	00:30	Х	
		4:00	Х	
C2D2		24:00	Х	
C2D8 (+/- 1 day)		168:00	Х	
C2D15 (+/- 1 day)		336:00	Х	
C2D22 (+/- 1 day)		504:00	Х	
C3D1	Pre-dose	00:00	Х	X
	EOI ^b	00:30	Х	
		4:00	Х	

Table 9.5-3:	Pharmacokinetic and Immunogenicity Sampling Schedule for BMS-986226
	(Parts B2 and C2)

Study Day of Sample Collection (1 Cycle = 4 Weeks)	Event	Time (Relative to Start of BMS-986226 Infusion) Hour:Min	BMS-986226 Blood Sample	BMS-986226 Immunogenicity Sample
C3D2		24:00	Х	
C3D8 (+/- 1 day)		168:00	Х	
C3D15 (+/- 1 day) [,]		336:00	Х	
C3D22 (+/- 1 day)		504:00	Х	
C4D1	Pre-dose	00:00	Х	X
C5D1	Pre-dose	00:00	Х	X
C7D1	Pre-dose	00:00	Х	X
Every 3 Cycles starting with C10D1 (example: C13D1, C16D1, etc)	Pre-dose	00:00	Х	Х
Adverse Event				
Grade 3/4 Hypersensitivity Reaction ^c			Х	X
End of Treatment and Follow-up Period				
EOT			Х	Х
30-Day FU			Х	Х
60-Day FU			Х	Х
100-Day FU			Х	Х

^a All pre-dose samples for BMS-986226 30 minutes).

should be taken prior to the start of nivolumab/ipilimumab infusion (preferably within

- ^b This sample should be taken immediately prior to the stopping of the second drug infusion (in combination therapy), preferably within 2 minutes prior to the end of infusion. If the end of infusion is delayed beyond the nominal infusion duration, the collection of this sample should also be delayed accordingly. EOI samples may not be collected from the same IV access as the drug was administered.
- ^c Samples will be taken as directed when drug-related adverse event, Grade 3/4 infusion reaction, or hypersensitivity reaction is confirmed.

Abbreviations: C = Cycle; D = Day; EOI = end of infusion; EOT = end of treatment; FU = follow-up.

Table 9.5-4:Pharmacokinetic and Immunogenicity Sampling Schedule for BMS-986226
(Parts D and E)

Study Day of Sample Collection (Cycle = 4 weeks)	Event	Time (Relative to Start of BMS-986226 Infusion) Hour:Min	BMS-986226 Blood Sample	BMS-986226 Immunogenicity Sample
Treatment Cycles				
Cycle 1 Day 1	Pre-dose ^a	00:00	Х	X
(C1D1)	EOI ^b	00:30	Х	
C2D1	Pre-dose	00:00	Х	X
C3D1	Pre-dose	00:00	Х	X
C4D1	Pre-dose	00:00	Х	Х
C7D1	Pre-dose	00:00	Х	Х
Every 3 Cycles starting with C10D1 (example: C13D1, C16D1, etc)	Pre-dose	0:00	Х	X
Adverse Event				
Grade 3/4 Hypersensitivity Reaction ^c			Х	
End of Treatment a	nd Follow-up	o Period		•
EOT			Х	X
30-Day FU			Х	X
60-Day FU			Х	Х
100-Day FU			Х	Х

- ^a All pre-dose samples for BMS-986226 should be taken prior to the start of nivolumab/ipilimumab infusion (preferably within 30 minutes).
- ^b This sample should be taken immediately prior to the stopping of the second drug infusion (in combination therapy), preferably within 2 minutes prior to the end of infusion. If the end of infusion is delayed beyond the nominal infusion duration, the collection of this sample should also be delayed accordingly. EOI samples may not be collected from the same IV access as the drug was administered.

^c Samples will be taken as directed when drug-related adverse event, Grade 3/4 infusion reaction, or hypersensitivity reaction is confirmed.

Abbreviations: C = Cycle; D = Day; EOI = end of infusion; EOT = end of treatment; FU = follow-up

The serum samples will be analyzed for drug (BMS-986226) and ADA (BMS-986226 antibodies and/or anti-nivolumab or anti-ipilimumab antibodies) by validated immunoassays.

Serum samples designated for PK

assessments may also be used for immunogenicity analysis if required (eg, insufficient volume for complete immunogenicity assessment or to follow up on suspected immunogenicity related AEs).

Labeling and Shipping of Biological Samples: Detailed instructions for the PK and PD blood collection, labeling, processing, storage, and shipping will be provided to the site in the procedure manual.

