7.1 Treatments Administered

The selection and timing of dose for each participant are presented in Table 7.1-1.

Table 7.1-1:Selection and Timing of Dose per Part

Study Treatment	Dose Level	Frequency of Administration	Route of Administration	Infusion time (Minute)
Preliminary Safety (Cohorts and Part A			
BMS-986226	2, 8, 25, 80, 200, 400, 800 mg	Q4W	IV	30
Part B1				
Nivolumab	480 mg	Q4W		30
BMS-986226	3 Doses evaluated by BLRM-copula, PK/PD	Q12W	IV	30
Part B2				
Nivolumab	480 mg	Q4W	IV	30
BMS-986226	3 Doses evaluated by BLRM-copula, PK/PD	Q4W	IV	30
Part C1				
Ipilimumab	3 mg/kg ^a	Q4W		30
BMS-986226	3 Doses evaluated by BLRM-copula, PK/PD	Q12W	IV	30

Revised Protocol No.: 04 Date: 31-May-2019

Study Treatment	Dose Level	Frequency of Administration	Route of Administration	Infusion time (Minute)
Part C2				
Ipilimumab	3 mg/kg ^a	Q4W		30
BMS-986226	3 Doses evaluated by BLRM-copula, PK/PD	Q4W	IV	30
Part D				
Nivolumab	480 mg	Q4W	IV	30
BMS-986226	PK/PD from Part B	TBD	1 V	30
Part E				
Ipilimumab	3 mg/kg ^a	Q4W	IV	30
BMS-986226	PK/PD from Part C	TBD	IV	30

Table 7.1-1:Selection and Timing of Dose per Part

^a Weight collected at baseline/screening should be used to calculate ipilimumab dose unless weight has changes more than +/- 10% from baseline on C1D1

Note: In Parts B, C, D, and E a 30-minute infusion of either nivolumab or ipilimumab will be followed by a 30-minute observation period, followed by a 30-minute infusion of BMS-986226. In all parts, participants will be observed for at least 60 minutes following the completion of BMS-986226 infusion due to the potential risk of, and to monitor for, infusion reactions.

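### Table 9.5-2 (Parts B1/C1) prints the end-of-infusion PK sample at 0:30 on the nivolumab/ipilimumab clock, an hour earlier than its own footnote b implies

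*Combined protocol and SAP*

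**What the plan says.** Four places bear on the timing of this sample.

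- **Table 9.5-2 (Parts B1 and C1), time column.** The header is "Time (Relative to Start of Nivolumab or Ipilimumab Infusion) Hour:Min". EOI is printed at 0:30 on C1D1, C4D1, C7D1 and C10D1. A further sample is printed at 4:00 on C1D1 and C4D1.
- **Table 7.1-1, note on the combination parts.** "a 30-minute infusion of either nivolumab or ipilimumab will be followed by a 30-minute observation period, followed by a 30-minute infusion of BMS-986226".
- **Table 9.5-2, footnote b, attached to the EOI rows.** "This sample should be taken immediately prior to the stopping of the second drug infusion (in combination therapy"). It adds that the draw moves later if the infusion ends late. The body text of Section 9.5 likewise ties the EOI sample "to the stopping of the second drug infusion (in combination therapy), preferably within 2 minutes prior to the end of infusion".
- **Tables 9.5-1, 9.5-3 and 9.5-4.** These also print EOI at 0:30, but their column is headed "Time (Relative to Start of BMS-986226 Infusion) Hour:Min".

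Section 10.3.3 lists Cmax among the PK parameters to be assessed and says that actual times will be used. PK parameter estimates are a secondary endpoint (Section 4).

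**The concern.** On the clock that Table 9.5-2 declares, 0:30 is a genuine end of infusion, but of nivolumab or ipilimumab. A study nurse working from the time column could draw the tube then, label it EOI, and be consistent with the printed schedule. The table measures BMS-986226, which has not been started at that point.

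Sections 5.5.1 and 5.1.2.4 give Parts B1 and C1 the job of informing the dosing schedule through PK and target-engagement data, and those data feed the dose and schedule for Parts D and E. A pre-infusion value filed as an end-of-infusion value would misstate the peak on that day. Analysing by actual time would reveal the error but could not supply a peak that was never sampled.

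**Working it through.** **Inputs.** Partner infusion 30 min, observation 30 min, BMS-986226 infusion 30 min (Table 7.1-1 note). Clock origin, EOI 0:30 and the 4:00 sample (Table 9.5-2). EOI drawn at the end of the second infusion, preferably within its last 2 minutes (footnote b, Section 9.5). Predicted half-life 25 days (Section 3.2.2.5). Infusions are assumed to run to their nominal lengths.

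**1. Reproducing the printed 0:30.** With the clock at the start of BMS-986226, EOI = 0 + 30 min = 0:30. This matches Tables 9.5-1, 9.5-3 and 9.5-4. It is not the origin that Table 9.5-2 states.

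**2. EOI on the clock in the Table 9.5-2 header.**
- BMS-986226 starts at 30 + 30 = 60 min, or 1:00.
- BMS-986226 ends at 60 + 30 = 90 min, or 1:30.
- The footnote b draw falls between 90 − 2 = 88 min and 90 min, or 1:28 to 1:30.
- The printed 0:30 is 60 − 30 = 30 min before BMS-986226 starts and 90 − 30 = 60 min before it ends.

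**3. What a sample at 0:30 would contain.** On C1D1 there has been no earlier dose, so it holds no BMS-986226. On C4D1, C7D1 and C10D1 it holds only what remains from doses given 12 or more weeks before.

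**4. Whether another sample covers the gap.**

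| Dosing day | Other post-dose sample that day | Next tabulated BMS-986226 sample |
|---|---|---|
| C1D1 | 4:00 | C1D2 |
| C4D1 | 4:00 | C4D2 |
| C7D1 | none | C8D1 pre-dose |
| C10D1 | none | C13D1 pre-dose |

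**5. The 4:00 samples.** On the header's clock, 4:00 − 1:00 = 3:00 after BMS-986226 starts, or 4:00 − 1:30 = 2:30 after it ends. In Parts A, B2 and C2 the same label means 4:00 after the start, or 4:00 − 0:30 = 3:30 after the end. The shift is one hour. With a half-life of 25 × 24 = 600 h, the terminal decline is ln 2 / 600 = 0.693 / 600 ≈ 0.1% per hour. Early distribution could add to that, but the documents give no rate for it.

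**6. Whether the header alone can be changed.** In Parts B1 and C1, BMS-986226 is given only on Day 1 of Cycles 1, 4, 7 and so on (Section 5.1.2). Nine rows of Table 9.5-2 fall in cycles without it: C2D1, C2D8, C2D15, C3D1, C5D1, C5D8, C5D15, C6D1 and C8D1. The C2D8 row is printed as 168:00, or 7 days. From the last BMS-986226 start it is 28 + 7 = 35 days, and 35 × 24 = 840 h. The 168:00 and 336:00 rows in Cycles 2 and 5 are right only from the partner infusion, which is given every cycle.

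**The case against.** The strongest reply is that EOI is an event, not a clock time. The row label, footnote b and the Section 9.5 text all direct the draw to the end of the second infusion, and a site drawing at 0:30 would contravene all three. Section 9.5 also defers collection details to a Laboratory Manual, which may remove the ambiguity and is not among the documents. If the sample is drawn correctly and only its nominal label is wrong, the use of actual times makes the harm small. All of this stands, and it limits the point to a risk of mistimed draws. It does not dispose of it: one tube should not carry two instructions an hour apart, and 0:30 is an easy misreading because some infusion does end then. Footnote b also does not reach the 4:00 rows.

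Three stronger readings are tempting, and the documents do not support them.

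- **That B1/C1 EOI samples contain no study drug and the peak is lost.** Nivolumab and ipilimumab are study treatment too (Section 7) and have just been infused at 0:30. What is absent is newly infused BMS-986226, and only if a site follows the column over the footnote. At C1D1 and C4D1 the 4:00 sample would still give an approximate Cmax.
- **That the header is the mistake because the other three tables use a BMS-986226 clock.** Tables 9.5-1 and 9.5-3 cover dosing every 4 weeks, and the Part D/E interval is still to be determined. For a 12-weekly drug with a 4-weekly partner, the partner clock is plausibly deliberate, and step 6 shows rows that need it.
- **That 36 participants are affected.** The planned size is 2 parts × 3 dose levels × about 6 evaluable = 36. That is not a ceiling, since up to 6 more may be added per combination and replacements are allowed. Nor is it a count of those affected, since not everyone reaches C7 or C10 and only mistimed draws matter.

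**Conclusion.** The inconsistency is real and lies wholly within the protocol. On the declared clock the printed EOI time is 60 minutes earlier than the draw that footnote b and Section 9.5 define, and 30 minutes before BMS-986226 begins. The possible consequence is a pre-infusion sample recorded as a peak. It is most serious at C7D1 and C10D1, where no other post-dose sample is taken that day. At C1D1 and C4D1 the consequence is softened by the 4:00 sample. The one-hour shift in the 4:00 samples is a minor misalignment between the 12-weekly and 4-weekly cohorts.

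The conclusion assumes nominal infusion and observation times, and that no Laboratory Manual instruction has already settled the matter. How often sites would follow the column rather than the footnote cannot be judged from the documents. The point merits correction because the sampling supports a secondary endpoint and the remedy costs almost nothing. It does not threaten the trial's primary safety objective.

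**What to change.** - Keep the partner-drug clock in Table 9.5-2, since the Cycle 2 and Cycle 5 rows without a BMS-986226 dose depend on it.
- Restate EOI as 1:30 at C1D1, C4D1, C7D1 and C10D1, and restate the 4:00 samples at C1D1 and C4D1 as 5:00 (1:00 + 4:00), which aligns them with Parts A, B2 and C2.
- Alternatively, use a BMS-986226 clock for the dosing-day rows only, and label the two clocks plainly. A change of header for the whole table should be avoided.
- Repeat the clarified draw time in the Laboratory Manual.
- In the PK data handling rules, flag any B1/C1 EOI sample whose actual time precedes the recorded start of BMS-986226, and do not treat it as an end-of-infusion value.

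The cost is a table correction, a manual note and one data check. No additional samples or visits are needed.
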